Title Study Phase	A Multicenter, Open-Label, 24-Week, Uncontrolled Study to Evaluate the Safety, Tolerability, and Pharmacokinetics of Oral Treprostinil Extended Release Tablets Following Transition from Remodulin or Inhaled Prostacyclin Therapy or as Add-on to Current PAH Therapy in De Novo Prostacyclin Pediatric Subjects Aged 7 to 17 Years with Pulmonary Arterial Hypertension Phase II
Indication	Pulmonary Arterial Hypertension (PAH)
Primary Objective	 To assess the safety and tolerability of oral treprostinil extended release tablets in three cohorts of pediatric subjects with PAH aged 7 to 17 years: Cohort 1: Subjects transitioning from intravenous (IV) or subcutaneous (SC) Remodulin[®] Cohort 2: Subjects transitioning from inhaled prostacyclin Cohort 3: As add-on to current PAH therapy in de novo prostacyclin subjects
Secondary Objective(s)	 To assess the effect of oral treprostinil on the following (assessed in all cohorts): Cardiopulmonary exercise testing (CPET) with progressive cycle ergometry Symptoms of PAH Panama functional classification WHO functional classification Six-minute walk distance (6MWD) (with oximetry and heart rate [HR] recovery monitoring) Borg dyspnea score Quality of life assessed via the Pediatric Quality of Life Inventory (PedsQLTM) questionnaire Plasma N-terminal pro-B-type natriuretic peptide (NT-Pro BNP) Cardiac magnetic resonance imaging (cMRI)
Study Design	Subjects with PAH aged 7 to 17 years. Multi-center, open-label, safety, tolerability and PK study of oral treprostinil in pediatric subjects with stable PAH aged 7 to 17 years who are, (1) transitioning from IV/SC Remodulin therapy; (2) transitioning from inhaled prostacyclin therapy; or (3) not currently receiving prostacyclin therapy.
Sample Size	Up to 40 pediatric subjects aged 7 to 17 years (25 transition [IV/SC Remodulin and inhaled] subjects and 15 de novo subjects)

Summary of	All Cohorts:
Subject Eligibility Criteria	Eligible subjects are between 7 and 17 years of age, inclusive, and have a diagnosis of PAH as confirmed by a previous right heart catheterization (RHC). Panama functional classification IIIb and IV subjects will be excluded.
	All subjects must be optimally treated (as determined by the Investigator) with background PAH therapies (e.g., phosphodiesterase type 5 inhibitor [PDE-5i], endothelin receptor antagonist [ERA], soluble guanylate cyclase [sGC]) for at least 90 days and have been on a stable dose without changes (except documented weight based adjustments) for at least 30 days prior to the first dose of oral treprostinil.
	 Cohort 1: Remodulin to Oral Treprostinil Transition Subjects must have been receiving IV/SC Remodulin for at least 90 days and at a stable dose for at least 30 days prior to the first dose of oral treprostinil. The IV/SC Remodulin dose will be between 25-75 ng/kg/min, inclusive, for the first five subjects enrolled in Cohort 1. Following a safety review by the Data Safety Monitoring Board (DSMB) after the first five Cohort 1 subjects have been enrolled and transitioned to oral treprostinil (study drug), the dose range may be expanded to 25-125 ng/kg/min, inclusive, for the remaining subjects.
	Cohort 2: Inhaled Prostacyclin to Oral Treprostinil Transition Subjects must have been receiving inhaled prostacyclin therapy for at least 90 days and at a stable dose for at least 30 days prior to the first dose of oral treprostinil.
	Cohort 3: Add-On to Current PAH Therapy in De Novo Prostacyclin Subjects must weigh at least 22 kg.

Drug Dosage and	All Cohorts:
Formulation	All subjects will receive study drug (oral treprostinil extended release tablets). The tablets may be provided as 0.125, 0.25, 1, or
	2.5 mg strengths. Oral treprostinil will be dosed three times daily (TID) or four times daily (QID) at the discretion of the Investigator, with food. Dosing will take place approximately every 6 to 8 hours for TID dosing, or approximately every 4 to 6 hours for QID dosing, with adjustments permitted based on the subject's lifestyle and schedule. Sudden dose escalation or reductions should be avoided as they may lead to intolerable adverse events (AEs) or worsening of PAH. Gradual dose titrations are recommended to reduce the risk to subjects.

Cohort 1: IV/SC Remodulin to Oral Treprostinil Transition

Dose Transition Schedule:

Once all entry criteria have been met and Baseline assessments completed, subjects will begin transition in the hospital from IV/SC Remodulin to oral treprostinil with a goal for complete transition off of IV/SC Remodulin within five days of the start of the transition. If possible, Day 5 (or last day of hospital stay, if transition occurred in less than 4 days) should be reserved as an observational period for subjects successfully transitioned to oral treprostinil and no longer receiving IV/SC Remodulin. Subjects will be discharged from the hospital after they have transitioned off IV/SC Remodulin, reached their target oral treprostinil dose, or as the Investigator feels appropriate. If necessary or appropriate per Investigator discretion, subjects can prolong or complete the transition in an outpatient setting for a total transition time of up to four weeks. A cross titration will occur so that the dose of IV/SC Remodulin is decreased as the dose of oral treprostinil is increased. Once subjects have been transitioned off IV/SC Remodulin, the dose of oral treprostinil may continue to be modified/titrated to the appropriate optimal dose for that subject throughout the rest of the study.

Cross Titration Dosing Guidelines:

- IV/SC Remodulin should not be decreased more than 30 ng/kg/min within a 24 hour period
- Oral treprostinil should be increased in proportion to Remodulin decreases and the subject's weight
- IV/SC Remodulin doses should be adjusted (i.e., decreased) at the same time oral treprostinil dose is increased

Cohort 2: Inhaled Prostacyclin to Oral Treprostinil Transition

Dose Transition Schedule:

Once all entry criteria have been met and Baseline assessments completed, dosing of oral treprostinil will be initiated at 0.125 mg TID or QID, at the discretion of the Investigator, with food. Dosing will take place approximately every 6 to 8 hours for TID dosing, or approximately every 4 to 6 hours for QID dosing, with adjustments permitted based on the subject's lifestyle and schedule. The first dose of 0.125 mg oral treprostinil should occur at the study site. Dose escalations may occur every 24 hours (following three or four consecutive doses, depending on TID or QID dosing, respectively) and should occur in increments of 0.125 mg TID or QID at the discretion of the Investigator during the first four weeks of the study as clinically indicated. Following four weeks of treatment, dose escalations may occur in either 0.125 mg or 0.25 mg increments every 24 hours, as tolerated. A cross titration will occur so that the doses of inhaled prostacyclin are decreased and the subject is fully transitioned off the inhaled prostacyclin by no later than Week 4.

Cohort 3: Add-On to Current PAH Therapy in De Novo Prostacyclin

Dose Schedule:

Once all entry criteria have been met and Baseline assessments completed, dosing of oral treprostinil will be initiated at 0.125 mg TID or QID, at the discretion of the Investigator, with food. Dosing will take place approximately every 6 to 8 hours for TID dosing, or approximately every 4 to 6 hours for QID dosing, with adjustments permitted based on the subject's lifestyle and schedule. The first dose of oral treprostinil should be taken at the study site. Dose escalations may occur every 24 hours (following three or four consecutive doses depending on TID or QID dosing, respectively) and should occur in increments of 0.125 mg TID or QID at the discretion of the Investigator during the first four weeks of the study as clinically indicated. Following four weeks of treatment, dose escalations may occur in either 0.125 mg or 0.25 mg increments every 24 hours, as tolerated.

Control Group	None
Route of Administration	Oral
Procedures	Up to seven study visits will occur during the 24-week study at the following time points: Screening, Baseline, Week 0 (Cohort 1 only; inpatient hospital stay Days 1-5), Week 3 Week 6, Week 12, and Week 24.

Screening/Baseline (All Cohorts):

All subjects will be assessed for eligibility during the 28 day screening period. Baseline assessments can be conducted over five days (120 hours) prior to the first dose of oral treprostinil, to allow for scheduling of all activities. The Screening and Baseline visits may be combined if all entry criteria are satisfied and all assessments are completed within five days (120 hours) prior to the first dose of oral treprostinil. The following assessments will be performed: vital signs, physical examination, six-minute walk test (6MWT)/Borg dyspnea score, CPET, 12-lead ECG, Panama and WHO functional classification assessments, symptoms of PAH, PedsQL, NT-Pro BNP, cMRI, clinical laboratory assessments, and safety assessments. Females of child bearing potential will undergo a urine pregnancy test. In addition, all subjects in Cohort 1will undergo an 8-hour PK assessment, which may occur up to seven days prior to the first dose of oral treprostinil (study drug). Pharmacokinetic assessments at Baseline will not be conducted in Cohort 2 or Cohort 3 subjects.

Transition Phase (Cohort 1):

Within five days (120 hours) of beginning Baseline assessments Cohort 1 subjects will undergo an inpatient hospital stay lasting approximately five days (Week 0) to transition from IV/SC Remodulin to oral treprostinil. The target transition goal is no longer than five days and for the subject to be completely transitioned off IV/SC Remodulin prior to discharge from the hospital. Subjects will be discharged from the hospital after they have transitioned off IV/SC Remodulin, reached their target oral treprostinil dose, or as the Investigator feels appropriate. If necessary or appropriate per Investigator discretion, subjects can prolong or complete the transition in an outpatient setting for a total transition time of up to four weeks.

The maximum time to titrate off IV/SC Remodulin is four weeks from the start of the transition; if the subject is not fully transitioned by Week 4, they will be removed from the study. If the subject is in the hospital during one of the scheduled study visits, the assessments for that visit should be conducted as scheduled during the defined visit window.

Treatment Phase (Cohort 2 and 3):

Following completion of Baseline assessments, the first dose of 0.125 mg oral treprostinil should be taken at the study site. Dosing of oral treprostinil will be initiated at 0.125 mg TID or QID, at the discretion of the Investigator, with food. Dosing will take place

approximately every 6 to 8 hours for TID dosing, or approximately every 4 to 6 hours for QID dosing, with adjustments permitted based on the subject's lifestyle and schedule. Dose changes should be conducted under appropriate medical supervision in consultation with the study site.

Dose Optimization/Evaluation Phase (All Cohorts):

	-
	Weeks 3, 6, and 12: Subjects will return to clinic for the following assessments: vital signs, 6MWT/Borg dyspnea score, Panama and WHO functional classification, symptoms of PAH, and safety assessments. At each visit, females of childbearing potential will undergo a urine pregnancy test. At Week 12, QOL (as measured by PedsQL Inventory) and clinical laboratory assessments, including NT-pro-BNP, will occur.
	Week 24 (or premature termination): Subjects will return to the clinic for the following assessments: vital signs, physical examination, 6MWT/Borg dyspnea score, CPET, 12-lead ECG, Panama and WHO functional class, symptoms of PAH, PedsQL, NT-Pro BNP, cMRI, clinical laboratory assessments, and safety assessments. Females of child bearing potential will undergo a urine pregnancy test. In addition, all subjects will undergo an 8-hour PK assessment.
Stopping Criteria	 Stopping Criteria: Unplanned hospitalization as a result of worsening PAH Clinically significant worsening in PAH symptoms or signs, which the Investigator feels requires a change of current therapy
	If one of these events occur within the four weeks following the first dose of oral treprostinil, the subject should be transitioned back to IV/SC Remodulin (for Cohort 1 subjects) and tapered off oral treprostinil, as appropriate, and discontinued from study. If any of these events occur after the first four weeks of the study, it is not required that a subject be removed from the study. The Investigator will determine whether it is safe for the subject to remain in the study.
	If two or more of the first five subjects in any cohort meet the stopping criteria, the data will be reviewed by the DSMB prior to enrolling additional subjects into that cohort.
Statistical Considerations	The study is not powered to test a null hypothesis. A sample size of 40 pediatric PAH subjects aged 7 to 17 years (25 transition [IV/SC Remodulin and inhaled] subjects and 15 de novo prostacyclin subjects) will enable a descriptive evaluation of the PK and an

_

	initial assessment of the safety and tolerability in this subject population for (1) transition from moderate to high doses of IV/SC Remodulin to oral treprostinil, (2) transition from inhaled prostacyclin to oral treprostinil, and (3) initiation of oral treprostinil as add-on therapy in de novo prostacyclin subjects.
	The safety and tolerability of transitioning subjects from IV/SC Remodulin to oral treprostinil (Cohort 1) or from inhaled prostacyclin (Cohort 2) will be based on the percentage of subjects successfully transitioning to oral treprostinil. A successful transition is defined as a subject from Cohort 1 or 2 who is receiving oral treprostinil and no longer receiving IV/SC Remodulin or inhaled prostacyclin, respectively at Week 4 and clinically maintained on oral treprostinil treatment through Week 24. A successful initiation of oral treprostinil (Cohort 3) will be defined as a subject who has been clinically maintained on oral treprostinil through Week 24.
	Analysis of secondary endpoints will be descriptive in nature. Numeric endpoints for post-Baseline assessments will be compared to Baseline using Wilcoxon signed rank test, and p-values will be calculated for descriptive purposes; no formal hypothesis testing is planned.
Sponsor	United Therapeutics Corp. [name]

TABLE OF CONTENTS

LIST	OF CONTACTS FOR STUDY	. 2
INVE	STIGATOR'S AGREEMENT	. 3
PROT	OCOL SYNOPSIS	. 4
TABI	LE OF CONTENTS	11
Table	of In-Text Tables	14
1 B.	ACKGROUND AND RATIONALE	15
1.1	DEFINITION OF CLINICAL PROBLEM.	15
1.2	ORAL TREPROSTINIL BACKGROUND	17
1.2.1	General Pharmacology	17
1.2.2	General Toxicology	18
1.2.3	Clinical Pharmacology	18
1.2.4	Clinical Trials Experience	20
1.3	RATIONALE FOR DEVELOPMENT OF STUDY DRUG IN	
	DISEASE/CONDITION	22
1.4	CLINICAL HYPOTHESIS	23
2 O	BJECTIVES	24
2.1	PRIMARY OBJECTIVE	24
2.2	SECONDARY OBJECTIVES	24
3 E2	XPERIMENTAL PLAN	25
3.1	STUDY DESIGN	25
3.2	OVERALL SCHEDULE OF TIMES AND EVENTS	27
3.3	CLINICAL ASSESSMENTS	34
3.3.1	Efficacy	34
3.3.1 3.3.1.	Efficacy 1 Cardiopulmonary Exercise Testing (CPET)	34 34

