2 OBJECTIVES

2.1 PRIMARY OBJECTIVE

To assess the safety and tolerability of oral treprostinil extended release tablets in three cohorts of pediatric subjects with PAH aged 7 to 17 years:

- Cohort 1: Subjects transitioning from IV/SC Remodulin
- Cohort 2: Subjects transitioning from inhaled prostacyclin
- Cohort 3: As add-on to current PAH therapy in de novo prostacyclin subjects

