3.3.2.5 Adverse Events

Adverse Events will be recorded throughout the course of the study from the time that each subject and/or caregiver signs the informed consent/assent form until the time screen failure is documented, or until the subject is either discontinued from the study or all Week 24 study assessments have been completed. Each subject/caregiver will be directly questioned for AEs at each scheduled study visit and during required telephone contacts. Subjects/caregivers will also be instructed to spontaneously report all AEs throughout the study. Additionally, a detailed collection of prostacyclin-related AEs will be captured via a standardized diary completed by the subject and/or caregiver each day of the five day inpatient hospital stay during the transition from IV/SC Remodulin to oral treprostinil or all subjects in Cohort 1.

All AEs should be followed until either resolution (or return to normal or baseline values), until they are judged by the Investigator to no longer be clinically significant, or for at least 30 days if the AE extends beyond the final study visit. All AEs meeting the criteria for serious (i.e., serious adverse events [SAEs]) should be followed until resolution, death, or the subject is lost to follow-up even if they are ongoing more than 30 days after completion of the final study visit.

All AEs/SAEs that occur while the subject is on oral treprostinil will be recorded as instructed in this protocol (Section 9.3).

If, at any time, the subject withdraws from the study and/or changes from study drug to commercially available Orenitram, any AEs/SAEs that occur on Orenitram (including product use errors, product quality problems, and therapeutic failures) will be reported following local post-marketing reporting requirements. These events will not be included in the eCRF.

Pulmonary arterial hypertension symptoms (Section 3.3.1.4) and PAH disease related events (Section 9.1.4) should only be recorded as an AE if the event is serious, new, or unusual with respect to intensity, frequency, or duration as compared to symptoms in the subject's medical history; or there is a reasonable possibility that the event was caused by the study drug.

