6.1.2 Cohort 2: Inhaled Prostacyclin to Oral Treprostinil Transition

Once all entry criteria have been met and Baseline assessments completed, dosing of oral treprostinil will be initiated at 0.125 mg TID or QID at the discretion of the Investigator, with food. Dosing will take place approximately every 6 to 8 hours for TID dosing or approximately every 4 to 6 hours for QID dosing, with adjustments permitted based on the subject's lifestyle and schedule. The first dose of 0.125 mg oral treprostinil should be taken at the study site. A cross titration will occur so that doses of inhaled prostacyclin will be decreased as oral treprostinil is increased. The transition must be completed by Week 4, or the subject will be withdrawn from the study.

Oral treprostinil dose escalations may occur every 24 hours (following three or four consecutive doses depending on TID or QID dosing, respectively) and should occur in increments of 0.125 mg TID or QID, at the discretion of the Investigator, during the first four weeks of the study as clinically indicated. Following four weeks of treatment, dose escalations may occur in either 0.125 mg or 0.25 mg increments every 24 hours, as tolerated. Sudden dose escalations or reductions should be avoided as they may lead to intolerable adverse effects or worsening of PAH. Gradual dose titrations are recommended to reduce the risk to subjects.

Routine contact between site personnel and the subject/caregiver should be conducted to monitor AEs and make decisions about dose titration between scheduled study visits. Dose

Version: Amendment 2_FINAL_01Sep2016

changes may be made at any time up until five days prior to the Week 24 visit. Week 24 visit assessments can be performed over five days (120 hours) if needed; however, no oral treprostinil dose adjustments are allowed from five days prior to the Week 24 study visit, unless required to protect subject safety. All dose changes will be documented and captured in the eCRF.

6.1.3 Cohort 3: Addition of Oral Treprostinil to Background PAH Therapy (De Novo Prostacyclin Subjects)

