8 STUDY TERMINATION

8.1 CRITERIA FOR SUBJECT WITHDRAWAL

A subject may voluntarily withdraw or be withdrawn from the study and/or oral treprostinil (study drug) by the Investigator at any time for reasons including, but not limited to, the following:

- Stopping criteria is met
- The subject wishes to withdraw from further participation
- A serious or life-threatening AE occurs or the Investigator considers that it is necessary to discontinue oral treprostinil (study drug) to protect the safety of the subject
- The subject deviated from the protocol
- The subject's behavior is likely to undermine the validity of his/her results
- Subject is female and became pregnant during the course of the study

TDE-PH-206

If a subject is discontinued from the study prematurely, the Investigator must provide an explanation in the eCRF and complete the End of Study Record for that subject. If oral treprostinil (study drug) has been administered, the Investigator should make every effort to perform all scheduled evaluations prior to discharge. In the event that a subject discontinues oral treprostinil prematurely due to an AE, the subject will be followed until either the Investigator determines that the AE has resolved, it is no longer considered clinically significant, the subject is lost to further follow-up, or for 30 days if the adverse event extends beyond the final visit.

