### 8.1 PREMATURE DISCONTINUATION AND MISSING DATA

Subjects may not complete the treatment period for a number of reasons, including but not limited to voluntary withdrawal, stopping criteria met, serious or life-threatening adverse event (AE), protocol deviation, behavior likely to undermine the validity of results, or pregnancy.

All available data from all safety subjects will be used as detailed in this SAP. Subjects will contribute the data available up to the point of study completion, or study discontinuation for any reason.

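### New adverse events that start after a child is discontinued for an incomplete switch at Week 4 or an early stopping event need not be collected, in a trial whose primary objective is safety

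*Protocol*

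**What the plan says.** The primary objective is safety: "To assess the safety and tolerability of oral treprostinil extended release tablets in three cohorts of pediatric subjects with PAH aged 7 to 17 years" (Protocol 2.1).

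Two rules take a child out of the study early.

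- **Week 4 rule.** For Cohort 1, "if the subject is not fully transitioned by Week 4, they will be removed from the study" (synopsis, repeated in Protocol 3.1, the Table 3-1 footnotes and 6.1.1). For Cohort 2, "The transition must be completed by Week 4, or the subject will be withdrawn from the study" (Protocol 6.1.2).
- **Stopping criteria in the first four weeks, any cohort.** According to the synopsis, "the subject should be transitioned back to IV/SC Remodulin (for Cohort 1 subjects) and tapered off oral treprostinil, as appropriate, and discontinued from study". Protocol 5.4 gives the corresponding rule. If the same events occur after four weeks, removal is not required.

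AEs are recorded "until the subject is either discontinued from the study" or until the Week 24 assessments are complete (Protocol 3.3.2.5 and the footnotes to Tables 3-1 and 3-2). SAP 11.3 ends collection at study termination. On analysis, SAP 8.1 says: "Subjects will contribute the data available up to the point of study completion, or study discontinuation for any reason". Protocol 10.3 agrees.

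Protocol 8.1 does distinguish leaving the study from leaving the drug: "A subject may voluntarily withdraw or be withdrawn from the study and/or oral treprostinil". Neither early-exit rule uses that distinction.

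SAP 11.4 lists deaths within 30 days of the last dose.

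**The concern.** Follow-up ends because the switch failed or the disease worsened, so the missing safety data are not missing at random. The period just after exit is also not a quiet one. The protocol itself warns that abrupt dose changes may worsen PAH (synopsis and 6.1.1), and Protocol 1.3 names line sepsis and rebound hypertensive crisis among the risks of approved prostanoid therapy. If a child has stopped oral treprostinil, has been discontinued and then has a new admission or dies, no rule brings that event into the database.

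The hypothesis in Protocol 1.4 is that children on Remodulin can be transitioned safely. A reader of the final report would see how many children failed and why, but not what newly happened to them afterwards. The DSMB review in Protocol 5.4, which is triggered by stopping-criteria cases, would have the same blind spot.

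**Working it through.** The plan states no figure on this point. The sample size (25 transition + 15 de novo = 40) has no alpha, power or effect size behind it, so there is no calculation to reproduce. The check is mainly a comparison of rules.

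**Step 1. Is an event captured, by when it starts?**

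- *While on oral treprostinil, including a taper or cross-titration back:* recorded (Protocol 3.3.2.5).
- *Before discontinuation and still open at exit:* followed. Non-serious AEs are followed until resolved, no longer clinically significant, or for at least 30 days past the final visit. SAEs are followed to resolution, death or loss to follow-up (Protocol 3.3.2.5, 9.3).
- *Between last dose and the Premature Termination visit:* captured if that visit falls after the last dose and before the discontinuation date. Protocol 7.4.6 allows the visit before stopping or as soon as possible after, and it includes AEs.
- *New event after discontinuation:* no collection rule in either document. The 30-day and until-resolution provisions concern events that have already begun.
- *Death within 30 days of last dose:* listed by SAP 11.4, but no protocol rule tells sites to look for deaths after discontinuation. A death that is the outcome of an open SAE would be found; another might not be.

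**Step 2. When does discontinuation fall?** The stopping rule names the return to Remodulin and the taper before discontinuation. The Week 4 rule gives no order. The length of the gap therefore depends on how each site dates exit relative to the return to prior therapy.

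**Step 3. Upper limit per child.** From Table 3-1, Week 4 is Day 29 and Week 24 is Day 169.

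169 − 29 = 140 days = 20 weeks; 20 / 24 = 83%.

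An earlier exit under the stopping rule leaves more than this unobserved; a later discontinuation date leaves less.

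**Step 4. Illustration across the 25 transition children.** The documents give no removal rate, so 10% to 30% is an assumption.

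- At 10%: 25 × 0.10 × 20 = 50 of 25 × 24 = 600 child-weeks, or 8.3%.
- At 30%: 25 × 0.30 × 20 = 150 of 600, or 25%.

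These are ceilings on unobserved time, mostly off study drug, and do not measure missed harm.

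**Step 5. Chance of missing at least one event.** With k children removed and probability p that each has a new event after exit, the chance is 1 − (1 − p)^k. Both inputs are assumed; p runs from 5% to 30%.

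- k = 1: 5% to 30%
- k = 2: 10% to 51%
- k = 3: 14% to 66%
- k = 5: 23% to 83%

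For scale, 0 events in 25 children has a one-sided 95% upper bound of 1 − 0.05^(1/25) = 11.3%. In a series this small, one or two unrecorded events would change the safety description.

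**The case against.** The case on the other side is substantial, and most of it limits the point.

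A reader might infer that events during the return to Remodulin are never recorded. The documents do not support that. The stopping rule puts the return and taper before discontinuation, everything on oral treprostinil is recorded, and the Premature Termination visit may follow the last dose. Also, a Cohort 1 child who fails at Week 4 is by definition still on some Remodulin, so a full re-start of lost therapy is not the typical picture.

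A reader might also infer that the trial will report a better success rate than is true. It will not. Success requires being off prior prostacyclin at Week 4 and maintained on oral treprostinil to Week 24 (Protocol 10.3.1, SAP 10.1), so a removed child cannot be a success. SAP 10.1 tabulates failures with reasons, and SAP 9.1 lists the stopping criteria met.

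Nor do the sickest children simply disappear. Every unplanned hospitalization is an SAE (Protocol 9.1.4) and is followed to its end, so for many stopping-criteria cases the index worsening remains an open event.

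Finally, recovery after a failed switch is not a listed objective, and this is a descriptive study of 40 children.

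What remains is the last gap in the chain: a new event after exit has no collection rule. None of these arguments fills it, and the 30-day death listing in the SAP assumes information that the protocol does not require sites to obtain.

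**Conclusion.** The point holds in a limited form. Cohort 1 and 2 children not fully transitioned by Week 4, and children in any cohort who meet a stopping criterion in the first four weeks, are discontinued from the study. New AEs and SAEs starting after that are not required to be collected or analysed.

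Any bias is confined to AE, SAE and death counts after exit. Those counts may be too low; the documents do not show that they will be, and the primary success percentage is unaffected. For a child removed at Week 4 the unobserved part is at most 20 of 24 weeks. The true size depends on how sites date discontinuation and on removal and event rates that the documents do not give. The point does not extend to a child who worsens after four weeks and is kept in the study.

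It is worth correcting because safety is the primary objective, the loss is caused by failure, and the remedy is cheap.

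**What to change.** Change data collection only. Leave the removal, stopping and dosing wording as it stands. Rewriting the Week 4 rule as removal from study drug would create a drug-stopping rule that the text does not contain.

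- **Protocol 3.3.2.5, 8.1, 9.3 and the AE footnotes to Tables 3-1 and 3-2:** state that for every dosed child discontinued early, new AEs and SAEs are collected for 30 days after the last dose of oral treprostinil, matching SAP 11.4. Say how this applies to a child who moves to commercial Orenitram, since 3.3.2.5 and 9.3 send those events to post-marketing reporting.
- **To Week 24, where consent continues:** record vital status, SAEs, PAH hospital admissions and current PAH therapy by brief telephone contact.
- **SAP 8.1 and 11.3:** include these data, and report events after the last dose in a separate table by cohort. The separation is needed because SAP 11.3 defines a TEAE by its start date alone, with no end, so late events would otherwise be mixed with on-treatment ones.

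The 30-day window alone covers 30 of the 140 days for a child whose last dose and exit are both on Day 29 (21%); the calls cover the rest.

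The cost is consent wording, an eCRF page, one SAP table and some calls for the children who discontinue. At the existing contact frequency a Week 4 exit means 8 weekly calls to Week 12 and 6 fortnightly calls to Week 24, 14 in all; a lighter schedule would serve. Some families may decline contact.
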